☐ The precise codes used in each study should be specified in study annexes.

Severity

The severity of the underlying conditions will be measured by the number of hospital admissions due to the underlying conditions in the year prior to study inclusion.

Smoking history

Smoking history will be collected and coded as 'never smoked', 'former smoker' (stopped smoking at least one year before inclusion in the study) and 'current smoker'.

Former vaccination

Former vaccination includes:

 Vaccination against influenza in the previous two years (collecting information on vaccination for each of the seasons).

Functional status (where applicable)

Information on functional status will be collected in terms of needing assistance with bathing.

Antiviral administration

Use of antivirals will be documented: type, dose and date of administration.

Other confounding factors that should be considered if available or relevant include:

- Level of social interaction
 - Number of household members
 - Children: nursery vs. school-age children
- Indicators of socio-economic status
 - Education level
 - Profession
 - Others (e.g. deprivation score by area of residence)
- Any other available and relevant for the study population

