3.5.8 Sample size

In a cluster investigation the number of cases available is often fixed, which limits the power of the study. Prior to the beginning of the study, calculations to determine the power of the study for detecting a given measure of effect with a set number of cases can be useful. This can also help determine if the control-to-case ratio needs to be increased to give more power.

Table 6 illustrates the various sample sizes that would ensure an alpha error of 0.05, a power of 0.8 or 0.9, a detectable odds ratio ranging from 0.3 to 0.6, and a vaccine coverage among the source population (or among controls) ranging from 50% to 70%.

The sample size should be respected for each population subgroup in which a sub- (stratified) analysis (e.g. effect modification) is planned.

Table 6: Sample size calculations

Power	Alpha	Controls/case	Vaccine coverage in source population/ controls	Detectable OR	Number of cases	Number of controls
0.90	0.05	1	50%	0.6	345	345
0.80	0.05	1	50%	0.6	262	262
0.90	0.05	1	50%	0.5	194	194
0.80	0.05	1	50%	0.5	148	148
0.90	0.05	1	50%	0.4	116	116
0.80	0.05	1	50%	0.4	89	89
0.90	0.05	1	50%	0.3	72	72
0.80	0.05	1	50%	0.3	56	56
0.90	0.05	1	60%	0.6	341	341
0.80	0.05	1	60%	0.6	259	259

Power	Alpha	Controls/case	Vaccine coverage in source population/ controls	Detectable OR	Number of cases	Number of controls
0.90	0.05	1	60%	0.5	188	188
0.80	0.05	1	60%	0.5	144	144
0.90	0.05	1	60%	0.4	110	110
0.80	0.05	1	60%	0.4	85	85
0.90	0.05	1	60%	0.3	67	67
0.80	0.05	1	60%	0.3	52	52
0.90	0.05	1	70%	0.6	370	370
0.80	0.05	1	70%	0.6	281	281
0.90	0.05	1	70%	0.5	200	200
0.80	0.05	1	70%	0.5	153	153
0.90	0.05	1	70%	0.4	115	115
0.80	0.05	1	70%	0.4	89	89
0.90	0.05	1	70%	0.3	68	68
0.80	0.05	1	70%	0.3	53	53

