3.5.11 Analysis

Analyses will be carried out separately for seasonal and pandemic vaccines and for different vaccine brands.

Separate analyses will be carried out for the different primary and secondary outcomes.

Analyses will be carried out including and excluding persons with recent respiratory symptoms (prior to cluster) that were not lab-confirmed, where information is available.

An analysis will be carried out including only persons 'fully vaccinated' in the vaccinated group. A second analysis will include persons 'fully' and 'partially vaccinated' in the vaccinated group.

Descriptive and univariable analyses

The proportion of eligible ILI cases and controls accepting to participate in the study is calculated (response rate).

Study participants are described by baseline characteristics. Baseline characteristics of cases and controls in unmatched studies are compared using the chi-square test, Fisher's exact test, t-test or the Mann-Whitney test (depending on the nature of the variable and the sample size). In matched case-control studies, characteristics of cases and controls are compared using McNemar's chi-square test, paired t-test, conditional logistic regression or the Wilcoxon signed-rank test (depending on the nature of the variable and the number of controls).

The association between vaccination status and baseline characteristics is assessed for both case and control groups.

Measure of effect

The vaccine effectiveness will be computed as VE = 1 - OR. An exact 95% confidence interval is computed around the point estimate.

Stratified analysis

Analysis will be stratified according to:

- age groups;
- presence or absence of high risk conditions.

A sufficient sample size should be planned in order to ensure sufficient individuals in each stratum. Studies should aim to have at least 80 cases and 80 controls in each of the strata. Effect modification is assessed by comparing the OR across the strata of the baseline characteristics. Confounding is assessed by comparing crude and adjusted OR for each baseline characteristic.

Multivariable analysis

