A multivariable (conditional, if matched) logistic regression analysis will be conducted to control for negative and positive confounding. Odds ratios and standard errors will be obtained. Preferably, the model will include: current influenza vaccination, former influenza vaccination, underlying chronic conditions, age, sex and smoking and functional status. Variables will be tested for multicollinearity. Interactions will be tested for using the Likelihood Ratio test (or Wald test) and included in the model if significant at 5% level. Factors other than statistical significance will also be used as criteria for inclusion of an interaction term.

4 Limitations

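### The preferred case-control adjustment model can be too large for the smaller Table 6 sizes; ordinary logistic regression then overstates VE by a few points (more if matched), and section 4 does not say so

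*Protocol*

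**What the plan says.** Protocol 3.5.11 (Multivariable analysis) states that a logistic model, conditional if the study is matched, will be fitted and will yield odds ratios and standard errors. On content: "Preferably, the model will include: current influenza vaccination, former influenza vaccination, underlying chronic conditions, age, sex and smoking and functional status". That is seven named terms, one of them the vaccine itself. It is worded as a preference, and the number of parameters is not given. The parallel cohort section, 3.4.11, leaves the model type and building strategy to study annexes; 3.5.11 contains no such deferral.

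The section on confounders fixes some of the coding. Smoking has three levels. Former vaccination covers two years, "collecting information on vaccination for each of the seasons". The Annex holds four separate chronic-condition variables.

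On size, the section headed Sample size concedes: "In a cluster investigation the number of cases available is often fixed, which limits the power of the study". Table 6 lists sizes that "would ensure an alpha error of 0.05, a power of 0.8 or 0.9", for "a detectable odds ratio ranging from 0.3 to 0.6" and control vaccine coverage of 50% to 70%. They run from 52 to 370 cases with one control per case. The stratified analysis adds: "Studies should aim to have at least 80 cases and 80 controls in each of the strata".

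Section 4.1 warns that small samples may lack power and precision. Section 4.6 warns of overestimated effectiveness, but only from high incidence combined with odds ratios.

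**The concern.** Maximum-likelihood odds ratios from a logistic model with few cases per parameter are pushed away from 1. For a protective vaccine this raises the estimated VE, and the push grows as covariates are added, without any confounding. A 1:1 matched conditional fit is more exposed, because pairs concordant on vaccination say nothing directly about the vaccine effect.

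At stake is the adjusted VE, which the Background says should inform vaccine recommendations. A local team following the template could read the rise from crude to adjusted VE as removal of negative confounding when part of it is a small-sample artefact. Nothing in section 4 would alert them.

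**Working it through.** **1. Reproducing Table 6.** Inputs from the table: two-sided alpha 0.05, power 0.80, control coverage p0 = 0.6, OR 0.3, equal groups. The plan's row is "0.80 0.05 1 60% 0.3 52 52".

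- p1 = OR·p0 / (1 − p0 + OR·p0) = 0.18 / 0.58 = 0.310; difference d = 0.290; mean proportion 0.455.
- Uncorrected n = [1.960·√(2·0.455·0.545) + 0.842·√(0.310·0.690 + 0.6·0.4)]² / d² = 45.2, rounded up to 46.
- With the continuity correction, n' = (n/4)·[1 + √(1 + 4/(n·d))]² = 51.9, rounded up to 52. This is the plan's figure.

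All 24 rows reproduce within 1 per group this way, and none does without the correction. Table 6 is therefore a crude two-proportion calculation with no covariate term.

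**2. Parameter count (assumption).**

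- Compact: vaccine 1, former vaccination 1, any chronic condition 1, linear age 1, sex 1, smoking 2, functional status 1 = 8.
- Fuller: vaccine 1, former seasons 2, Annex conditions 4, four age groups 3, sex 1, smoking 2, functional status 1 = 14.

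**3. Cases per parameter.**

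| Cases | 8 parameters | 14 parameters |
|---|---|---|
| 52 | 6.5 | 3.7 |
| 56 | 7.0 | 4.0 |
| 80 | 10.0 | 5.7 |
| 89 | 11.1 | 6.4 |
| 148 | 18.5 | 10.6 |
| 345 | 43.1 | 24.6 |

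With 14 parameters, 9 of the 24 rows are at 7 or below and 12 are above 10. With 8, only 3 are at 7 or below.

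For random 1:1 pairs at 50% coverage, the share discordant on vaccination is p1(1 − p0) + p0(1 − p1) = 0.5. So 56 pairs give about 28 discordant pairs: 3.5 per parameter with 8 and 2.0 with 14. For 148 pairs the figures are 74, 9.3 and 5.3. For 345 pairs they are about 172, 21.6 and 12.3.

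**4. Size of the bias.** Simulation with 1,500 to 4,000 data sets per scenario, modest assumed covariate effects, ordinary maximum likelihood and Wald 95% intervals. Ranges span differing assumed covariate effects.

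| Design | True VE | Median VE, 8 par. | Median VE, 14 par. | Interval coverage |
|---|---|---|---|---|
| 56/56 unmatched | 70% | 73% | 74–76% | 93–94% |
| 80/80 unmatched | 70% | 71.9% | 73.9% | 94.7%, 93.1% |
| 80/80 unmatched | 60% | – | 63.4% | 93.7% |
| 56 pairs | 70% | 77% | 83–84% | 94%, 90–92% |
| 89 pairs | 60% | 64–65% | 67–68% | 94%, 92% (one run) |
| 148 pairs | 50% | 52–54% | 53–54% | 96%, 94% (one run) |
| 345 pairs | 40% | 40.9% | 41.4% | 96%, 95% |

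Unmatched, at 148 to 345 cases, the excess is about 0 to 3 points. With true OR 1 and 14 parameters, median VE is off by 0.3 points at 52/52 and 0.5 at 80/80. At 56 cases with 14 parameters, maximum likelihood failed or diverged in 3–5% of data sets.

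**5. After the fix.** Firth-penalised unmatched fits brought median VE within about 2 points of the truth, with coverage of about 95–98%. Penalised conditional fits gave medians of 69.6–70.0% (true 70%), 59.1–60.4% (true 60%) and 49.9–51.0% (true 50%), with coverage of 95–97%.

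**The case against.** The strongest reply is that the protocol does not order a 14-parameter model on 52 cases. This stands. The covariate list is a preference, functional status is tied to clusters of elderly people, and the Annex lets teams add or drop variables. Where the text describes how chronic disease is used, it is mostly as a yes/no risk group, which is the compact coding. Table 6 is illustrative, and half its rows leave more than 10 cases per parameter even with 14 parameters. A reader might also push the count to 17 by adding the other vaccine, disease severity and antivirals, but those are factors to be considered, not stated model terms.

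The 80/80 aim applies to each stratum. Two strata give at least 160 cases for an overall model, about 11 per parameter with 14, and the text does not say the multivariable model is fitted within strata.

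The shift is also small beside the noise. At 56/56, OR 0.3 and 50% coverage, the crude 95% interval runs from about VE 32% to 87%, and section 4.1 warns of imprecision. That is fair for one study, but imprecision has no direction and this error does.

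The arithmetic mean of unmatched VE is off by only about −2 to +2 points at the table's odds ratios. That is weak reassurance, because 1 − OR is skewed. At true OR 1 and 52/52, where the log-OR bias is negligible, mean VE is 16 points too low.

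Finally, fitting details often belong in an analysis plan. Here, though, 3.5.11 states the model without deferring it, so a later plan would have to override it.

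**Conclusion.** The point holds conditionally. With rich coding and about 52 to 89 cases, or a model fitted inside one 80/80 stratum, ordinary logistic regression overstates median VE by about 2 to 7 points unmatched and about 3 to 14 points in 1:1 matched fits. Interval coverage is mostly about 91–95%. At 148 or more cases the excess is about 0 to 3 points unmatched and up to about 4 matched.

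This rests on an assumed parameter count, assumed modest covariate effects, random pairing in the matched case and Wald intervals, which the text implies but does not name. The bias is on the median or log-OR scale.

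A reader might infer that every adjusted case-control VE under this protocol is inflated by up to 14 points, or that its intervals fail badly. The documents do not support that. The upper figure needs about 56 matched pairs with all 14 parameters, and matching factors would drop out of such a model. Under-coverage is mild, and some scenarios show none. I rate this a cheap improvement.

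**What to change.** In 3.5.11, state that when cases (or discordant pairs, if matched) per model parameter are few, for example below about 10, the adjusted VE is estimated by Firth-penalised logistic regression, or penalised conditional likelihood if matched, with penalised profile-likelihood intervals. In that situation use compact coding: one high-risk yes/no and one former-vaccination yes/no. Report the number of cases or discordant pairs per parameter beside each adjusted VE. Add small-sample bias away from the null to section 4.1.

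The cost is a few sentences and standard software. The downsides are slight shrinkage, slightly conservative intervals and coarser confounder adjustment. In large samples the penalised and ordinary fits converge, so larger studies lose little.

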4.1 Sample size

An investigation of a cluster often has a fixed sample size that can be low. It is possible that the study will not have enough power to give a precise estimate of IVE in overall or stratified analysis.

4.2 Negative confounding

These are biases showing that high risk groups are more likely to be vaccinated, therefore reducing VE. Negative confounding will be minimised by taking into account the presence of chronic diseases in the adjustment and by stratifying by risk group, if sample size allows.

4.3 Positive confounding

These are biases reflecting a healthy vaccinee effect. People with a healthy behaviour and a good functional status are more likely to accept/request vaccination, therefore increasing the measured VE.

Positive and negative confounding are minimised through stratification and multivariable analysis, including presence of chronic diseases and variables collected to measure positive and negative confounding. We cannot rule out the presence in the study population of characteristics leading to positive or negative confounding for which information is not collected in the study questionnaire. Therefore, residual positive or negative confounding may be present. A sensitivity analysis will be conducted to assess the effect of a potential unmeasured confounding factor.

4.4 Misclassification bias

Notification of a cluster is often not prompt. This can lead to a delay between onset of illness and laboratory confirmation, which can result in misclassification of cases. If the swabbing delay is associated with vaccination status, then the IVE can be over- or underestimated. If this misclassification is irrespective of vaccination status, it can, under certain conditions, reduce test power lead bias study estimators to the null value.

4.5 Inclusion of persons with A(H1N1)v infection prior to the outbreak

While information on A(H1N1)v infection prior to outbreak is recommended to be collected, reliable information on this might not be available. Depending on the nature of the vaccine, including persons with previous illness could result in lowering the IVE estimates.

4.6 Overestimation of IVE

If the incidence of A(H1N1)v infections is high in the cluster/outbreak and a traditional case-control study design is used – or a cohort design using logistic regression to obtain ORs – then the IVE may be overestimated.

5 Consent

According to country-specific regulations, informed (oral or written) consent will be required from each participant into the study.

☐ The type of consent (oral/written) should be specified in study annexes.

6 Dissemination of results

Each study team will specify how the results will be disseminated.

Dissemination of results should be specified in study annexes.

7 Logistical aspects

For each cluster investigation, a principal investigator needs to be appointed. For secondary attack rate in household analyses, a system of notification of index cases within households needs to be determined (e.g. sentinel network of GPs).

Computer support needs to be in place.

For each cluster investigation, the study group applies specific criteria to identify the relevant laboratories for RT-PCR, culture and sequencing. Key points to be taken care of include:

- sampling materials;
- transport;
- quality assurance; and
- funding of laboratory tests.

8 Budget

Key components include:

- study team;
- laboratory;
- IT support, programming.
- A detailed budget, specifying which part of the budget will be requested from ECDC, should be outlined in the study annexes.

References

- Centers for Disease Prevention and Control (CDC). Interim within-season estimate of the effectiveness of trivalent inactivated influenza vaccine Marshfield, Wisconsin, 2007–08 influenza season. Morb Mortal Wkly Rep 2008 Apr 18;57(15):393-8.
- Farrington CP. Estimation of vaccine effectiveness using the screening method. Int J Epidemiol 1993 Aug; 22(4):742-6.
- Farrington CP. Re: "The effect of disease prior to an outbreak on estimates of vaccine efficacy following the outbreak". Am J Epidemiol 1996 143(9):961.

vacc_05	Numeric (categorical)	0 = No 1 = Yes 8 = Don't know	Previous influenza vaccination 2005–6
vacc_04	Numeric (categorical)	0 = No 1 = Yes 8 = Don't know	Previous influenza vaccination 2004–5
Diabetes	Numeric (categorical)	0 = No 1 = Yes 8 = Don't know	Diabetes and endocrine
heart_dis	Numeric (categorical)	0 = No 1 = Yes 8 = Don't know	Heart disease
immune	Numeric (categorical)	0 = No 1 = Yes 8 = Don't know	Immunodeficiency and organ transplant
Lungdis	Numeric (categorical)	0 = No 1 = Yes 8 = Don't know	Lung disease
Severity	Numeric (count)	integer	Number of hospitalisations in the previous year for the chronic disease
fs_bath	Numeric (categorical)	0 = No 1 = Yes 8 = Don't know	Requires assistance to bath
Pregnant	Numeric (categorical)	0 = No 1 = Yes 8 = Don't know	Pregnancy status
Smoking		0 = Never 1 = Former 2 = Current 9 = Don't know	Never, former (stopped smoking at least one year before inclusion in the study), current smoker
Antivir	Numeric (categorical)	0 = No 1 = Yes 8 = Don't know	Recent use of antivirals
Antivirdate	Date	dd/mm/yyyy	Date of antiviral administration
Antivirdose	Text		Doses of antiviral taken
Antivirbrand	Text		Type of antiviral taken (brand name)
ili_prior	Numeric (categorical)	0 = No 1 = Yes 8 = Don't know	ILI since beginning of pandemic, but prior to cluster
Ili_prior_lab	Numeric (categorical)	0 = Negative 1 = Positive 2 = Not done 8 = Don't know	Laboratory result (positive/negative)
ili_prior_virus	Text		Laboratory result: virus type and subtype of recent ILI
contra	Numeric (categorical)	0 = No 1 = Yes 8 = Don't know	Exclusion criteria: contraindication for influenza vaccination

This table represents a selection of covariates. Variables can be included or excluded as necessary.

Other annexes containing details of specific studies should be added to the current protocol.

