3.4.2 Study participants

If the cluster has a manageable population size, the whole study population will be eligible for the VE study. If the population is very large and the attack rate is high, then a systematic or random sample of this population should be selected for the study.

A sample size calculation should be detailed in study-specific annexes.

¹ Orenstein WA, Bernier RH, Dondero TJ, Hinman AR, Marks JS, Bart KJ, et al. Field evaluation of vaccine efficacy. Bull World Health Organ 1985;63(6):1055-68.

Exclusion criteria

Study participants are excluded if they are not eligible for vaccination with the pandemic/seasonal vaccine because of having a condition listed in the summary of products characteristics (e.g. anaphylactic hypersensitivity to eggs or its components), or if they refuse participation. People with laboratory-confirmed diagnosis of A(H1N1)v infection since the beginning of the pandemic (or other date according to the duration of the pandemic) and prior to the beginning of the outbreak/cluster of influenza are excluded as they are not at risk.

People who were not swabbed but had respiratory symptoms in the interval from the beginning of the pandemic (or other date according to the duration of the pandemic) and prior to the beginning of the outbreak/cluster will be documented and analyses carried out including and excluding them.

Reasons for exclusion must be documented.

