3.4.10 Data

Data collection

Data will be collected from all study participants using a standardised questionnaire. The procedures to collect data should be defined by each study coordinator (e.g. face-to-face, by telephone, postal questionnaire, web-based, etc.).

Double data entry is needed.

Details on data collection methods, data entry and data transmission should be specified in study annexes.

Information collected

(see Annex)

- Study participant demographics
- Signs, symptoms
- Severity: hospitalisation, pneumonia, death
- Date of onset of symptoms
- Date of swabbing
- Laboratory results
- Selected underlying chronic conditions (including diabetes, heart disease, chronic obstructing pulmonary disorder and immunodeficiencies);
- Number of hospitalisations in the previous year (if relevant)
- Number of GP visits in the previous year (if relevant)
- Smoking history
- Current influenza vaccination(s) including date of vaccination, type (seasonal, pandemic), doses and brand (if possible)
- Former influenza vaccination
- Functional status (if relevant)
- Pregnant: yes/no (if relevant)
- Use of antivirals, type, dose and date of administration
- Information on respiratory symptoms or laboratory-confirmed A(H1N1) influenza since the beginning of the pandemic in their country (or other date according to the duration of the pandemic) and prior to the cluster/outbreak

Data validation

If data are collected using paper questionnaires, a sample of paper questionnaires should be checked against the study database to validate data entry.

The specific validations procedures should be specified in study annexes.

Data cleaning

Summary and frequency tables and graphic displays of appropriate variables will be used to find illegal, implausible or missing values within the dataset. Checks for inconsistencies will be carried out (e.g. date of swabbing before date of onset of symptoms). These values will be checked against the questionnaires or queried

with the study participant. Any changes to the data will be documented and stored separately from the crude database. Any recoding of data (e.g. age from date of birth) will be documented.

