3.4.11 Analysis

Analyses will be carried out separately for seasonal and pandemic IVE and for different vaccine brands.

Separate analyses will be carried out for the different primary and secondary outcomes.

Analyses will be carried out including and excluding persons with recent respiratory symptoms (prior to cluster) that were not lab-confirmed, where information is available.

An analysis will be carried out including only persons 'fully vaccinated' in the vaccinated group. A second analysis will include persons 'fully' and 'partially vaccinated' in the vaccinated group.

Descriptive and univariable analyses

Participation variables include:

- total number not eligible
- total number eligible
- total number included: vaccinated and unvaccinated; and
- total number of subjects that refused participation.

Study population baseline characteristics by influenza vaccination status

Baseline characteristics include:

- Age
- Gender
- Socio-economic status indicators
- Comorbidities
- Functional status (if relevant to cluster)
- Pregnancy status
- Previous vaccination (influenza)
- Antiviral use
- Smoking history

Baseline characteristics of vaccinated and unvaccinated participants will be described using proportions and mean/medians (depending on variable type). Missing data for each characteristic will be described, along with approaches on how the missing data were dealt with.

In order to test for differences between vaccinated and unvaccinated characteristics, Student's t test, Mann-Whitney test, chi-square test or Fisher's exact test will be used (depending on the nature and the sample size).

Table 4: Study population baseline characteristics by influenza vaccination status:

(to be completed/modified according to the variables collected)

Characteristics	Vaccinated (N =)	Unvaccinated (N =)
Demographic		
Age		
• Sex		
 Socio-economic status 		
Comorbidities		
Functional status (if relevant)		
Pregnancy status		
Previous flu vaccination		
Antiviral use		
Smoking history		

Crude VE estimates

The vaccine effectiveness will be computed as $VE = (1 - RR) \times 100$; exact 95% CI are computed around the estimate for each outcome.

Stratified analysis

Analysis should be stratified according to:

- age groups;
- presence or absence of high risk conditions;
- effect modifiers are assessed one by one comparing the RR across the strata of the baseline characteristic;

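### The Annex asks about earlier ILI only, which is narrower than the respiratory-symptom rule that the include/exclude analysis depends on

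*Protocol*

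**What the plan says.** For the cohort design, section 3.4.2 sets two rules about illness before the cluster. The first excludes "People with laboratory-confirmed diagnosis of A(H1N1)v infection since the beginning of the pandemic", if the diagnosis came before the outbreak; no ILI condition is attached. The second concerns "People who were not swabbed but had respiratory symptoms in the interval from the beginning of the pandemic": they are to be documented and analysed both ways. Section 3.5.5 repeats both rules for controls.

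The analysis sections (3.4.11 and 3.5.11) restate the second rule: "Analyses will be carried out including and excluding persons with recent respiratory symptoms (prior to cluster) that were not lab-confirmed, where information is available".

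The data sections (3.4.10 and 3.5.10) list as information to collect "Information on respiratory symptoms or laboratory-confirmed A(H1N1) influenza since the beginning of the pandemic in their country", under a pointer to the Annex.

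The Annex has three variables for this history:
- ili_prior: "ILI since beginning of pandemic, but prior to cluster"
- Ili_prior_lab: a laboratory result, with a code for not done
- ili_prior_virus: "Laboratory result: virus type and subtype of recent ILI"

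**The concern.** The body of the protocol speaks of respiratory symptoms, while the Annex speaks of ILI. Sections 3.4.6 and 3.5.4 define ILI by three joint conditions, so it is a strict subset of respiratory illness. The excluding analysis cannot be run as described if the only field that identifies the group covers part of it.

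At stake is the protocol's own check on a bias that it names. Section 4.5 warns that "including persons with previous illness could result in lowering the IVE estimates", depending on the nature of the vaccine. Comparing the two analyses shows whether this matters in a given cluster. If some earlier illness stays in both analyses, the comparison will understate the sensitivity of VE to it. No later analysis plan can recover history that was never asked for.

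**Working it through.** **Setting the texts side by side.** No stated figure in the protocol depends on this point, so there is none to reproduce.

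- Take a person who had cough and sore throat before the cluster, with gradual onset and no systemic symptom, and was not swabbed. Under 3.4.2 this person belongs to the group analysed both ways. Under the Annex, ili_prior is correctly coded 0, and no other Annex field records the illness. The person stays in the excluding analysis.
- Take a person with laboratory-confirmed A(H1N1)v infection before the cluster whose illness did not meet ILI. Under 3.4.2 (or 3.5.5 for a control) this person is excluded. The laboratory fields carry the ILI prefix and the virus field refers to the recent ILI, so it is unclear where the result should be entered.
- During the cluster the protocol is broader: any one of the listed signs and symptoms leads to swabbing, and the Annex records symptoms one by one. Only the earlier history is reduced to ILI.

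**Illustration of size.** All inputs are assumptions, since the documents give none:
- true RR 0.5, so true VE 50%;
- qU and qV, the shares of unvaccinated and vaccinated people infected before the cluster, 5% to 20%;
- s, the share of those earlier infections that met ILI and are therefore removed, 0.4 to 0.8;
- earlier infections that are not removed confer full immunity.

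Among those who remain, the share still susceptible in a group is f = (1 − q) / [(1 − q) + q(1 − s)]. The observed VE is 1 − 0.5 × fV/fU.

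Example with qU = 20%, qV = 5%, s = 0.4:
- fU = 0.80/(0.80 + 0.12) = 0.8696
- fV = 0.95/(0.95 + 0.03) = 0.9694
- VE = 1 − 0.5 × 0.9694/0.8696 = 44.3%

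| qU / qV | VE, s = 0.4 | VE, s = 0.8 |
|---|---|---|
| 20% / 5% | 44.3% | 48.0% |
| 20% / 10% | 46.1% | 48.6% |
| 10% / 5% | 48.3% | 49.4% |
| equal (10% / 10% or 20% / 20%) | 50.0% | 50.0% |
| 5% / 10% | 51.6% | 50.6% |
| 10% / 20% | 53.6% | 51.3% |

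The mirror image of the first row, 5% / 20%, swaps fU and fV. At s = 0.4 it gives 1 − 0.5 × 0.8696/0.9694 = 55.1%. With s = 1, every row returns 50.0%.

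**The case against.** The best defence is that this is a core template. The Annex closes by saying that its table is a selection which teams may add to or cut, and sections 3.4.10 and 3.5.10 already ask for the broader item. A team working from those sections would collect the right history, so it does not follow that such people will be missed in every study. That stands, and it makes this an inconsistency with an easy repair. It does not remove the inconsistency: the same sections send the reader to the Annex for the variables, and nothing there says that the field is narrower than the rule. The qualifier in 3.4.11 about available information covers history that cannot be obtained. It does not cover history lost through the wording of a question.

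Several stronger readings are tempting, and the documents do not support them:

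- *That earlier confirmed infection is not captured at all.* Ili_prior_lab exists, and no skip rule makes it conditional on ili_prior. The link to ILI rests on the variable names and the label of the virus field.
- *That everyone with earlier symptoms should be removed.* Section 3.4.2 limits the group to unswabbed people and analyses them both ways.
- *That the people missed are no longer at risk.* The protocol says this only of laboratory-confirmed infection. An unswabbed person with a cough may not have had A(H1N1)v.
- *That they are likelier to be unvaccinated, so VE is biased downward.* No passage says so. Section 4.5 says only that IVE could be lowered.
- *That VE would read 47%, 44% or 38% instead of 50%.* These figures follow from 1 − 0.5/(1 − qU) with qU = 5%, 10% and 20%. They assume no earlier immunity among the vaccinated and count all of these immune people as unidentified, so they show one direction only.

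**Conclusion.** The inconsistency holds. The field ili_prior is narrower than the rule it serves in 3.4.2, 3.4.11, 3.5.5 and 3.5.11, and narrower than the item listed in 3.4.10 and 3.5.10. Used as written, it leaves earlier non-ILI respiratory illness in the excluding analysis. The laboratory part is weaker: a field exists, but its labelling ties it to an ILI episode.

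Neither the size nor the direction of the effect on VE can be fixed from the documents. In the scenarios tabulated, the error runs from about 6 points too low to about 4 points too high, and reversing the widest imbalance takes the upper end to about 5. It vanishes when earlier infection is equally common in both groups. These figures rest on the assumed true VE, infection shares and ILI detection, and on full immunity after earlier infection. They concern the risk ratio of the cohort design.

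**What to change.** Reword ili_prior to record any respiratory symptom between the start of the pandemic and the start of the cluster, and keep ILI as a sub-item. Relabel the earlier laboratory result and virus fields so that they record any earlier laboratory-confirmed A(H1N1)v infection, whether or not the illness met ILI. The Annex then matches the exclusion, data and analysis sections for both designs.

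The cost is a few Annex lines and the matching questionnaire items. The change must be made before data collection. It does not reach earlier infections without symptoms or a test, so the caution in 4.5 should stay.
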